1. PURPOSE OF THIS MANUAL

This operations manual is a guide for participation in this clinical trial. All members of the study are responsible for following the procedures stipulated in this operations manual. Detailed

specifications and study procedures are provided for consistency in protocol adherence amongst participating clinics.

2. INTRODUCTION

2.1 Background

Multiple sclerosis (MS) is a common cause of severe neurological disability in young adults, resulting from an autoimmune interruption of both myelin and axons within the central nervous system (CNS). The diagnosis is made by fulfilling both spatial criteria, by meeting the requisite number of lesions within the brain or spinal cord, along with criteria for time, by demonstrating a history of at least a second clinical attack or the development of a new MS lesion on MRI after the seminal neurological event^{2, 3}. Similar to many other chronic diseases, signs of impending disease may be observed in the months to years preceding the formal diagnosis. In the case of MS, healthy individuals who do not exhibit signs of neurological dysfunction commonly have brain MRI studies performed for a reason other than an evaluation for MS that reveal unexpected anomalies highly suggestive of demyelinating plaques given their size, location, and morphology^{1, 4, 5}. These healthy subjects lack symptomatology suggestive of MS and fulfill formal criteria for radiologically isolated syndrome (RIS), a recently described MS subtype that expands upon the phenotype of at-risk individuals for future demyelinating events. A formal description of RIS was first introduced in 2009¹, to define this relevant cohort of individuals routinely encountered in clinical practice. The discovery of such anomalies creates intersecting neuro-ethical, legal, social, and practical medical management quandaries and is, therefore, of both immediate and long-term clinical significance. Despite advancements in the characterization of RIS subjects⁶⁻⁹, and in our understanding of risk factors for initial symptom development^{10, 11}, the effect of treatment on such cases remain unclear. In addition, disease-modifying therapies are currently being recommended and prescribed outside of controlled clinical trial settings, placing subjects at risk for unnecessary exposure to both expensive and potentially harmful treatments.

2.2 Purpose & rationale

The purpose of this investigation is to systematically study the efficacy of Tecfidera in those individuals who possess incidental white matter anomalies within the brain following a MRI study that is performed for a reason other than for the evaluation of MS. A recent multi-national effort, involving RIS subjects from 5 countries, revealed that in 16% (73/451) of cases, regardless of the presence or absence of an asymptomatic spinal cord focus, a disease modifying therapy was prescribed prior to the development of a first clinical event¹². Despite the intention by clinicians to prevent disease progression and the biological plausibility of altering the demyelinating course, there are no scientific data supporting the use of such treatments in RIS. The rationale for the proposed research is that earlier treatment intervention may extend the time to the first acute or progressive clinical event resulting from CNS demyelination and reduce new radiologic activity. In addition, exposure to earlier treatment compared to traditional treatment patterns in symptomatic groups may result in more profound effects on reducing disability progression long-term.

3. STUDY OBJECTIVES

3.1 Primary objective

The primary objective of this study is to assess the time from randomization to the first acute or initial neurological symptom resulting in a progressive clinical course related to CNS demyelination in those treated and untreated with Tecfidera.

Definitions:

Acute neurological event: The development of an acute neurological episode localized to the optic nerve, brainstem, cerebellum, spinal cord, or long sensory or motor tracts, lasting > 24 hours followed by a period of symptom improvement.

Progressive event: The onset of a clinical symptom (e.g. leg weakness) with the temporal profile revealing at least a 12-month progression of neurological deficits.

3.2 Secondary objectives

The secondary objectives of this study include the change in the number of new or enlarging T2 lesions, contrast enhancing lesions, T2-lesion volumes, and brain atrophy at End of Study.

3.3 Exploratory outcomes

Exploratory outcomes will include differences in cognitive performance and PRO between active treatment and placebo groups.

4. ORGANIZATION OF THE STUDY

4.1 Organizational Structure

The organizational structure of the clinical trial will consist of 15-20 clinical sites throughout the United States.

4.2 Clinical Centers

Each clinical center will be responsible for recruitment, treatment, evaluation of participants, and collection of study data according to the protocol. The Principal Investigator will direct each clinical center and each site will designate a study coordinator, manager, or regulatory specialist, where applicable. The roles and responsibilities of the study staff are described below. In addition, each center will consist of appropriate support personnel trained in human subject protection and HIPAA guidelines for research.

4.3 Principal Investigator (PI)

The Principal Investigator will be responsible for the overall conduct of research activities at the site, including:

- Conduct the study in accordance with the current protocol.
- Supervise the described investigation(s).
- Ensure that the requirements relating to obtaining informed consent and institutional review board (IRB) review and approval are met.
- Submit all adverse experiences that occur in the course of the investigation via electronic data capture (EDC) for submission by the sponsor.
- Ensure that all associates, colleagues, and employees assisting in the conduct of the study are informed about their obligations in meeting the above commitments.
- Maintain adequate and accurate records and to make those records available for inspection.
- Promptly report to the IRB all changes in the research activity and all unanticipated problems involving risks to human subjects or others.
- Make no changes in the research without IRB approval except where necessary to eliminate apparent immediate hazards to human subjects.

4.4 Site Personnel: Clinical Research Project Manager, Regulatory & Contracts Specialist, & Study Nurse/Coordinator

A well-implemented protocol is often attributable to an organized, responsible study coordinator. The PI may delegate some or all of the following tasks to the study coordinator, regulatory specialist, and/or project manager. Under the PI's guidance, this person(s) may:

- Prepare regulatory documentation.
- Ensure the study is conducted in compliance with protocol requirements.
- Maintain IRB correspondence and regulatory documentation.
- Recruit potentially eligible subjects and evaluate them for protocol eligibility.
- Ensure that informed consent has been obtained from the participants before initiating any research-related activity.
- Schedule tests and appointments for participants within timeframes required by protocol.
- Complete Case Report Forms (CRFs) accurately.
- Collect data in accordance with the protocol.
- Maintain source documentation for each study participant in accordance with the protocol.
- Instruct and educate participants regarding study intervention modalities and anticipated side effects and their management.
- Monitor participant compliance.
- Identify and document adverse events and serious adverse events.
- Initiate Serious Adverse Event Reports (SAEs) and obtain the PI's signature within 24 hours, complete proper documentation notify proper individuals and fax report according to protocol.
- Identify and document protocol deviations.
- Respond to data queries in a timely manner.

5. STUDY PROCEDURES

5.1 Hypothesis

We hypothesize that treatment with Tecfidera will i) extend the time to the first acute or progressive demyelinating event by reducing CNS autoimmune inflammation and ii) reduce the development of new MRI lesions within the CNS compared to subjects randomized to placebo.

5.2 Central Clinical and Imaging Units

To accurately identify subjects with RIS, formal units will be created to review data prior to study entry.

5.2.1 Core Clinical Unit:

A Core Clinical Data Unit, led by [name], will be formed and comprised of a prominent international collaborator and trained MS specialist. This group will evaluate clinical information from both existing and new cases within partnering centers, including results from para-clinical studies (i.e. blood work, CSF, electrophysiological studies, etc.) to ensure that subjects accurately fulfill criteria for study entry. In addition, this group will be responsible for adjudicating all neurological events and post-attack clinical data during the study period. If a discrepancy exists between reviewers following the independent review of submitted cases, [name] will provide a decision on the final classification. The Core Clinical Unit will unify all screening data (including conclusions from the Central Imaging Unit (below)) and will notify participating site PIs when entry criteria are met for potential study participants.

5.2.2 Central Imaging Unit:

A Central Imaging Unit will be formed and will be comprised of a board certified neuro-radiologist and MS specialist with neuro-imaging expertise. The MS specialist will confirm screened cases for study entry. MRI scans from subjects will be independently reviewed by the MS specialist and neuro-radiologist and determinations made if subjects fulfill MRI criteria for RIS. If a discrepancy exists between the two reviewers following the independent review of a case the MS specialist with neuro-imaging expertise will provide a decision on the final classification. The MS specialist with neuro-imaging expertise will also be responsible for

ensuring that a uniform protocol (“Dummy scans”) is implemented at specified sites for the collection of uniform, multi-center data for post processing. In addition, this group will evaluate all MRI studies of the CNS for interval change (i.e. new and enlarging T2 lesion(s), gadolinium enhancement) during follow-up imaging studies and imaging studies acquired during clinical events. At End of Study, changes in T2-lesion volumes, and brain atrophy (SIENA) will be determined.

5.3 Study Design

This is a multi-center, randomized, double-blinded study in which approximately 90 RIS subjects (refer to section 12 for sample size justification) will be treated with either Tecfidera or placebo (1:1 randomization) for 3 years or until End of Study (EOS) which is March 31, 2021. The primary outcome measure is the time to the first acute or progressive neurological event resulting from CNS demyelination. The secondary outcome measures include the number of new or enlarging T2 lesions, and the change in the number of contrast enhancing lesions, and T2-lesion and brain volumes. Study participants, along with the treating and examining physicians, will be blinded to treatment assignment. Central Clinical and Imaging Units will screen all potential study subjects for inclusion/exclusion criteria. We expect to enroll all RIS subjects within the U.S.

Following informed consent and verification of entry criteria by the core units, study participants will be randomized 1:1 to either Tecfidera (120mg by mouth twice daily for 7 days with dose escalation to 240mg by mouth twice daily) or placebo. Clinical follow-up by the treating physician, as defined within this protocol, will occur at weeks **0, 48, 96, 144 and/or EOS** and during or immediately following clinical exacerbations. (please refer to Study Schematic). During clinical visits comprehensive medical history data, safety labs, and optional biological samples will be obtained by the treating physician.

Patients will be scheduled for safety screenings (CBC & CMP) at weeks **12, 24, 72, 120**; at which time they will be seen by research coordinator or research nurse.

In addition to the face-to-face visits described above, study participants will be contacted over the telephone at weeks **4, 8, 36, 60, 84, 108, and 132** to assess for medical or treatment difficulties in addition to study medication compliance.

Standardized MRI studies of the brain will be performed at weeks 0 ,96, 144 or EOS; an additional MRI will be obtained at week 46 for those patients enrolled at the UTSW site only. Clinical imaging studies of the brain and/or spinal cord performed during or immediately following the onset of a clinical exacerbation will be performed at the discretion of the site PI with scan costs covered under the medical standard of care. A clinical MRI of the cervical spinal cord with and without contrast will be recommended to study participants at week 0 and week 144 as medical standard of care.

Participants who cannot receive contrast due to allergic reaction or abnormal blood counts will not be excluded from the study. Their imaging studies without contrast will be accepted.

All reported acute or progressive clinical events will be adjudicated by the Central Clinical Unit. Clinical visits due to suspected exacerbations associated with CNS demyelination, and associated diagnostic studies and treatments, will be covered under the medical standard of care by third party payers. A recommendation to re-evaluate the patient within 3 months following the clinical event to assess for extent of recovery will be made.

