12.1 Power calculation

A Bayesian approach has been used to calculate the sample size. The Bayesian approach is based on combining a prior distribution for the treatment effect with the result of the trial (which represents here the likelihood). The prior distribution for the effect of Tecfidera vs. placebo was built using the data from DEFINE and CONFIRM trials in RRMS.

12.1.1 Parameter estimates for the rate of events in the RIS cohort in a Bayesian framework

The parameters for the expected treatment effect of a 50% reduction in the risk of the first clinical event are $HR=0.50$ (i.e. $\log HR=-0.69$). A SD for $\log HR$ is set to 2.2 to get a power of 80% to detect a 50% reduction in the hazard of events with 80 patients per arm (original design). This base scenario is set in order to use the same assumptions done as for the original calculations.

Several scenarios were considered to allow a sensitivity analysis for the power calculations.

12.1.2 Parameters for the prior distribution – Scenario 1

The 2 arms treated with Tecfidera are pooled together (i.e. same efficacy)
Patients from DEFINE and CONFIRM are classified as “early RRMS” if they had:

- No previous treatment
- Less than 5 years from disease onset
- EDSS≤1.5

| | Placebo | Tecfidera | Total |
|-------|---------|-----------|-------|
| RRMS | 703 | 1372 | 2075 |
| Early | 68 | 157 | 225 |
| Total | 771 | 1529 | 2300 |

225 patients are classified as Early in the 2 trials merged.

Treatment effect in the “Early” group ($HR=0.24$, risk reduction=76%) $\log HR=-1.45$; $SE=0.31$.
Treatment effect in the rest of RRMS ($HR=0.59$, risk reduction 41%)

The parameters of the prior distribution, according to the Tecfidera effect in early RRMS in the DEFINE+CONFIRM studies, are: mean=-1.45, SD=0.31.

12.1.3 Parameters for the prior distribution – Scenario 2

The 2 arms treated with Tecfidera are pooled together (i.e. same efficacy)
We take the Tecfidera effect form the merged trials: $HR=0.58$, risk reduction=42%; $\log HR=-0.548$; $SE=0.073$.

The parameters of the prior distribution, according to the Tecfidera effect all the patients included in the DEFINE+CONFIRM studies, are: mean=-0.548, SD=0.073.

12.1.4 Parameters for the prior distribution – Scenario 3

The 2 arms treated with Tecfidera are pooled together (i.e. same efficacy)
We take the Tecfidera effect from the merged trials: HR=0.58, risk reduction=42%

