We assume the treatment effect on the RIS cohort to be reduced by 20% since there is a portion of RIS that are not subclinical MS.

HR=0.58*1.20 =0.70

logHR=-0.36

mean=-0.36, SD=0.073.

12.1.5 Parameters for the prior distribution – Scenario 4

The 2 arms treated with Tecfidera are pooled together (i.e. same efficacy)
We take the Tecfidera effect from the merged trials: HR=0.58, risk reduction=42%; SE=0.073

We assume the treatment effect on the RIS cohort to be reduced by 30% since there is a portion of RIS that are not subclinical MS.

HR=0.58*1.30 =0.75; logHR=-0.282; mean=-0.282, SD=0.073

We report here the different power estimates for a sample size of 80 RIS patients (40 per arm) according to the 4 scenarios and 4 different assumptions on SD (representing those observed multiplied by 2, 3, 4 and 5).

| | Prior HR | Parameters for the prior | SD | | | |
|--|-----------------|----------------------------------|------|--------|--------|-----|
| | | | x2 | x3 | x4 | x5 |
| Scenario 1 (early RRMS, subgroup of the trials) | HR=0.235 | Prior mu=-1.45, SD=0.31 | 86% | 70% | 63% | 9% |
| Scenario 2 (all RRMS in the trials) | HR=0.58 | Prior mu= -0.548, SD=0.07 | 100% | 99.60% | 91.30% | 80% |
| Scenario 3 (all RRMS with an effect diluted by 20%) | HR=0.70 | Prior mu= -0.362, SD=0.07 | 99% | 86% | 70% | 61% |
| Scenario 4 (all RRMS with an effect diluted by 30%) | HR=0.75 | Prior mu= -0.282, SD=0.07 | 96% | 67% | 56% | 49% |

Overall, the power analysis shows that the projected sample size of 80 patients should result in adequate power for the majority of scenarios considered.

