13. TIMELINE ESTIMATE

- Contracting completion to IRB approval: 7 months
- Last patient in: September 30, 2019
- Last patient out: March 31, 2021
- Study completion and submission of final manuscript for publication: September 1, 2021

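### Section 5.3 enrols about 90 on the strength of section 12, but section 12 gives power only for 80, and that power rests on a prior the primary log-rank test does not use

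*Protocol*

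**What the plan says.** - **Enrolment target (Protocol 5.3).** The trial plans "approximately 90 RIS subjects (refer to section 12 for sample size justification", randomized 1:1.
- **Base calibration (12.1.1).** The SD for the log hazard ratio "is set to 2.2 to get a power of 80% to detect a 50% reduction in the hazard of events with 80 patients per arm". The protocol marks this as the original design and explains: "This base scenario is set in order to use the same assumptions done as for the original calculations".
- **Power table (12.1.5).** "We report here the different power estimates for a sample size of 80 RIS patients (40 per arm", for four priors taken from two RRMS trials, each with its SD multiplied by 2, 3, 4 and 5.
- **Conclusion (12.1.5).** "the projected sample size of 80 patients should result in adequate power for the majority of scenarios considered".
- **Primary analysis (Synopsis, Data analysis).** Kaplan-Meier curves for time from randomization to first demyelinating event, with groups compared by log-rank test. Bayesian Cox models appear only under the secondary analyses.

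**The concern.** A reader who follows the pointer from 5.3 to section 12 looks for the justification of 90 and finds one for 80. Neither section explains the 10 extra patients, so it is unclear whether 90 is a dropout allowance, a later increase or a leftover figure.

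The second difficulty is the kind of power reported. Section 12.1 defines it by combining a prior for the treatment effect with the trial result. The primary comparison named in the Synopsis uses the trial data alone. The closing statement on adequacy therefore describes a different procedure from the planned test, and nothing in section 12 shows what that test can detect at 80 or 90 patients.

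**Working it through.** **Inputs.** HR 0.50, so |log HR| = 0.693, and SD 2.2 (12.1.1). Sizes: 80 per arm (12.1.1), 40 per arm (12.1.5), 45 per arm (half of 90, 5.3). Priors as printed in the table. Alpha and the Bayesian success rule are not stated; I assume two-sided 5% and a 95% posterior interval excluding HR = 1.

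**Step 1: reproduce the base case.** Take SE = 2.2/√(n per arm) and power = Φ(0.693/SE − 1.96). At 80 per arm, SE = 0.246 and power is 80.5%, against 80% stated. Two alternatives do not fit: SE = 2.2·√(2/80) gives 51.3%, and one-sided 5% gives Φ(2.818 − 1.645) = 88%. So 2.2 acts as a per-patient scale.

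**Step 2: reproduce the table.** With prior mean m and prior SD s (printed SD times the multiplier), a normal prior and a normal estimate give

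power = Φ( SE × [0.693/SE² + |m|/s² − 1.96·√(1/s² + 1/SE²)] ).

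Example, scenario 3 ×4 at 40 per arm: s = 0.28 and SE = 0.348, so the bracket is 5.73 + 4.62 − 8.99 = 1.36, and Φ(0.348 × 1.36) = 68%. The table prints 70%.

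| Scenario | Printed (×2/×3/×4/×5) | Recomputed, 40 per arm | Recomputed, 45 per arm |
|---|---|---|---|
| 1 | 86/70/63/9 | 85.5/68.6/61.2/57.7 | 87.1/72.1/65.4/62.1 |
| 2 | 100/99.6/91.3/80 | 100/99.4/90.3/78.4 | 100/99.5/91.7/81.5 |
| 3 | 99/86/70/61 | 99.9/85.4/68.2/60.2 | 99.9/87.9/72.9/65.4 |
| 4 | 96/67/56/49 | 96.0/66.4/54.7/51.2 | 96.7/71.8/60.8/57.2 |

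At 40 per arm, 14 of 16 cells agree within 2 points. The exceptions are scenario 4 ×5 (51.2 against 49) and scenario 1 ×5 (57.7 against 9, possibly a lost digit). At 45 per arm 8 of 16 agree, and at 80 per arm 3 of 16. One-sided 5% matches only 3 of 16 at 40 per arm. These counts use the SD of 0.07 printed in the table. The 0.073 in the text fits less well (8 of 16 at 40 per arm, 9 of 16 at 45). The fit does not separate 40 from 41 or 42 per arm, but the protocol states 40.

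**Step 3: effect of 90 against 80.** Column differences run from 0 to 6.1 points (largest at scenario 4 ×4: 60.8 − 54.7), all in favour of 90. Cells at 80% or more number 8 of 16 as printed, 7 of 16 recomputed at 40 per arm (scenario 2 ×5 falls to 78.4) and 8 of 16 at 45.

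**Step 4: power of the log-rank test without a prior.** Use the formula in step 1, with events d from SE² = 4/d, so d = 4n/2.2² for n per arm.

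| n per arm | SE | Events | Power |
|---|---|---|---|
| 40 | 0.348 | 33 | 51.3% |
| 45 | 0.328 | 37 | 56.1% |
| 80 | 0.246 | 66 | 80.5% |

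If one-sided 5% were intended, despite the poor fit above, the first two become Φ(1.993 − 1.645) = 64% and Φ(2.114 − 1.645) = 68%.

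**Step 5: weight of the prior.** In scenarios 2 to 4 even the widest prior has SD 5 × 0.07 = 0.35, about the SE of the whole trial at 40 per arm (0.348). It therefore counts for roughly as much as the trial's own data. The prior closest to flat, scenario 1 ×5 (SD 1.55), recomputes to 57.7%, near the prior-free 51.3%.

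**The case against.** The strongest reply has four parts.

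- **The target is only approximate, and the error is on the safe side.** The direction is right: 90 exceeds 80 and section 12 slightly understates prior-based power for it. A reader might infer that the mismatch leaves the trial underpowered; step 3 shows it does not. But an approximate target does not absorb 10 patients when the same sentence cites a section that never mentions 90.
- **The 80 per arm is openly a superseded reference.** This stands. A reader might take the 80% as claimed for the current trial, but the protocol labels it as the original design and tabulates separate figures for 40 per arm.
- **Calibrating the SD at 80 per arm is not a fault.** This also stands. A reader might infer that 2.2 was applied at the wrong size; the table reproduces with 2.2/√40, so it was rescaled properly.
- **A Bayesian sample size is a legitimate choice, and the table shows how power falls as the prior widens.** Granted as to the method. It does not answer the point that the named primary test takes no prior, nor that the conclusion is unqualified.

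A further reading would be that the fixed end date ("Last patient out: March 31, 2021", with last entry on September 30, 2019) cuts power further, because late entrants are followed for less than 144 weeks. The protocol gives no event rate and no accrual pattern, so neither the size nor the net direction relative to the calibrated SD can be established. I make no claim on it.

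**Conclusion.** The point holds in two limited parts. First, the enrolment target of about 90 has no matching power statement: section 12 justifies 80, and the protocol does not connect the two. This is a mismatch in a figure the trial relies on, in the conservative direction, worth about 0 to 6 points of prior-based power. Second, the statement of adequate power depends on an informative prior. For the log-rank test named as primary, the protocol's own inputs give about 51% at 80 patients and 56% at 90.

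These figures assume two-sided 5%, a normal approximation, and the reading of 2.2 as a per-patient scale, which the base case and 14 of 16 table cells support. Severity is moderate: internal consistency and stated power, not a faulty calculation and not underpowering caused by the 80/90 gap.

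**What to change.** 1. State one target in 5.3 and section 12.
2. If it is 90, rerun the table at 45 per arm (the last column in step 2 shows what to expect). If 90 is 80 plus an allowance, say so and name its basis and rate: 10/90 = 11%.
3. State alpha and the success rule. Beside the table, give the expected events and prior-free log-rank power for the chosen size (33 events and 51% at 80, or 37 events and 56% at 90, under two-sided 5%).
4. Reword the conclusion so that adequacy is said to depend on the prior.

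The cost is protocol wording and a short recalculation. No extra patients and no change to conduct are needed. Table entries rise slightly if rerun at 45 per arm; the added prior-free figure is less favourable than the present conclusion suggests.

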- Multivariate Bayesian Cox regression models will be created to assess the independent predictive value of demographic characteristics (i.e. sex, ethnicity, age at the time of RIS diagnosis), clinical data (i.e. MS family history, occult neurological examination findings, environmental exposure data, cognitive performance, PRO, CSF profiles, etc.), and imaging data (i.e. number of brain MRI lesions, the presence of gadolinium enhancing lesions, geographical distribution of lesions, involvement of the spinal cord, brain atrophy, etc.) on the time to the first symptomatic event.
- The association of each covariate with time to the first clinical symptom will be quantified by hazard ratios (HR) along with their 95% confidence intervals (CI). Assessments to determine differences between centers will also be performed with statistical adjustments planned for subsequent analyses depending upon the obtained results.
- MRI outcomes (proportion of subjects with gadolinium enhancement and new radiologic activity).

ABOUT THIS STUDY

A strategic research alliance was formed between the Radiologically Isolated Syndrome Consortium (RISC) and Biogen to explore this important initiative of investigating the impact of early treatment intervention in subjects who possess the first visible manifestation of multiple sclerosis. This collaboration enabled the development and effective execution of an innovative approach in demyelinating disease more quickly and strategically. The current home of RISC, the University of Texas Southwestern Medical Center at Dallas (Texas, U.S.A.) is proud to serve as the study sponsor for this novel research study.

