12.3. Analysis of other variables

To validate the association between incidentally identified anomalies within the CNS that are highly suggestive of MS and seminal demyelinating events, systematically acquired environmental exposure, clinical, and radiological, data will be assimilated in an effort to identify significant risk factors. We will evaluate the time from the initial MRI revealing incidental anomalies to the first demyelinating event (acute or initial symptom resulting in a progressive clinical course) or new MRI focus utilizing Kaplan-Meier survival analyses. Log-rank tests will be used to compare survival data between groups at univariate analysis. Multivariate Bayesian Cox regression models will be created to assess the independent predictive value of demographic characteristics (i.e. sex, ethnicity, age at the time of RIS diagnosis), clinical data (i.e. MS family history, occult neurological examination findings, environmental exposure data, CSF profiles, cognitive performance, etc.), and imaging data (i.e. number of brain MRI lesions, the presence of gadolinium enhancing lesions, geographical distribution of lesions, involvement of the spinal

cord, brain atrophy, etc.) on the time to the first symptomatic event. The association of each covariate with time to the first clinical symptom will be quantified by hazard ratios (HR) along with their 95% confidence intervals (CI). Assessments to determine differences between centers will also be performed with statistical adjustments planned for subsequent analyses depending upon the obtained results. Corrections to co-variables will be made when necessary if baseline differences are detected.

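### The enhancing-lesion outcome is defined as a change in count; the follow-up count with the week-0 count as a prespecified covariate would be more precise at almost no cost

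*Protocol*

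**What the plan says.** Protocol section 5.3 gives the number of new or enlarging T2 lesions as a plain count, then adds "and the change in the number of contrast enhancing lesions, and T2-lesion and brain volumes". Section 3.2 puts every MRI measure under one word: "the change in the number of new or enlarging T2 lesions, contrast enhancing lesions, T2-lesion volumes, and brain atrophy at End of Study". Neither section names the reference scan. Week 0 is implied by the imaging schedule in 5.3: "Standardized MRI studies of the brain will be performed at weeks 0 ,96, 144 or EOS".

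The synopsis, under secondary analyses, describes enhancement differently: "MRI outcomes (proportion of subjects with gadolinium enhancement and new radiologic activity". That is a proportion of subjects, not a change in a count.

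No section names a test or model for the MRI outcomes. The only statement on baseline adjustment is the general one in section 12.3: "Corrections to co-variables will be made when necessary if baseline differences are detected". Section 5.3 also allows scans without contrast for participants who cannot receive it: "Their imaging studies without contrast will be accepted". Some participants will therefore lack an enhancing-lesion count at one or both scans.

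**The concern.** Enhancement is transient. A count at week 0 may say little about the count a year and a half or more later. If so, subtracting the baseline count removes little real between-patient variation and adds the baseline count's own variance to the treatment contrast. A chance difference between arms in baseline lesions also passes in full into the estimate.

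The trial has only 40 to 45 participants per arm (sections 12.1.5 and 5.3), and fewer new MRI lesions is the second part of its hypothesis (section 5.1). Precision on this outcome is worth protecting when the covariate is already being collected.

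The wording also limits the analysis. A change in count can be negative, so it cannot be the response in a count model, which is the natural choice for a sparse, skewed lesion count.

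**Working it through.** **Inputs from the protocol.** Planned size is about 90 (45 per arm) in section 5.3, and 80 (40 per arm) in the power section. Last patient in is 30 September 2019 and last patient out is 31 March 2021 (section 13). That is 548 days, or 548/7 = 78 weeks, the shortest gap between baseline and End of Study for a participant who completes. Early-withdrawal scans can come sooner.

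**Not in the protocol.** It gives no correlation, SD, lesion mean or power figure for any MRI outcome, so there is no stated figure to reproduce. The power table in section 12.1 concerns the primary outcome only. Everything numerical below rests on assumed values.

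**Step 1: direction.** Let SD0 and SD1 be the baseline and follow-up SDs and rho their correlation. Up to a common factor, the variance of the treatment contrast is:
- unadjusted change: SD1² + SD0² − 2·rho·SD0·SD1
- follow-up adjusted for baseline: SD1²·(1 − rho²)

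The difference is (SD0 − rho·SD1)², which is never negative. The direction therefore needs neither equal SDs nor a known rho.

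**Step 2: size with equal SDs.** The ratio is 2(1 − rho)/(1 − rho²) = 2/(1 + rho).

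| rho (assumed) | change | follow-up alone | adjusted | change / adjusted |
|---|---|---|---|---|
| 0 | 2.0 | 1 | 1.00 | 2.00 |
| 0.2 | 1.6 | 1 | 0.96 | 1.67 |
| 0.5 | 1.0 | 1 | 0.75 | 1.33 |
| 0.95 | 0.10 | 1 | 0.0975 | 1.03 |

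The change score is noisier than the unadjusted follow-up count only when rho is below 0.5 (in general, below SD0/(2·SD1)). Against the adjusted analysis it is less precise at every rho below 1.

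**Step 3: skewed counts.** Lesion counts are not normal, and an effective treatment lowers the follow-up SD. A simulation used overdispersed counts with mean 0.5, 40 per arm and a true rate ratio of 0.5 (all assumed). The adjusted analysis was linear. The SEs of the treatment difference were:

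| rho in untreated arm | SE, change | SE, adjusted | SE reduction | variance ratio |
|---|---|---|---|---|
| 0 | 0.2873 | 0.1885 | 34% | 2.32 |
| 0.14 | 0.2670 | 0.1767 | 34% | 2.28 |
| 0.29 | 0.2537 | 0.1773 | 30% | 2.05 |
| 0.48 | 0.2192 | 0.1693 | 23% | 1.68 |

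The variance ratios exceed 2/(1 + rho) because the treated arm's follow-up SD is smaller.

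**Step 4: power.** A second simulation had 45 per arm, stronger overdispersion, a true halving and 600 runs per setting. Power rose from 10.7% to 16.7% (mean 0.3, rho about 0) and from 16.0% to 24.7% (mean 0.6, rho about 0.35). It is low either way.

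**Step 5: chance imbalance.** A baseline difference of d lesions between arms moves the change estimate by d. The appropriate correction is rho·(SD1/SD0)·d. With equal SDs, rho 0.2 and d = 0.1, that is 0.02, so the change score overcorrects by 0.08. The true difference in the Step 3 simulation was 0.25.

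**Step 6: cost of the covariate.** The variance inflation is about 1 + 1/(N − 4): 1 + 1/76 = 1.013 at N = 80 and 1 + 1/86 = 1.012 at N = 90.

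**The case against.** The strongest reply is that the protocol names outcomes, not analyses. A linear model of change with baseline as covariate gives the same treatment estimate and SE as a model of the follow-up value with baseline as covariate, and an analysis plan that is not shown may specify exactly that. This stands. A reader might infer that the protocol commits to an unadjusted change-score test, and it does not. The equivalence holds only for linear models, however, so the change definition still shuts out a count model. The one adjustment rule on paper is triggered by the data rather than prespecified.

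It can also be said that change need not mean follow-up minus baseline, since section 3.2 applies the word to new or enlarging T2 lesions, which are already an interval measure. That is a fair reading, and it is a further reason to state the outcome exactly.

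Three stronger inferences are not supported:
- **Bias.** A participant with many baseline lesions tends to improve by regression to the mean, but with 1:1 randomisation this acts on both arms alike. The contrast is not biased in expectation.
- **A known loss.** The size depends on rho, which the protocol does not give.
- **T2 volume.** Section 5.2.2 says "At End of Study, changes in T2-lesion volumes, and brain atrophy (SIENA) will be determined". If rho for volume is 0.95 to 0.98, adjustment lowers the variance of the change score by only 1 to 2.5%, about what the extra degree of freedom costs. Scoring volume as change is not a precision problem.

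**Conclusion.** The point holds for the enhancing-lesion outcome, as a conditional one. If that outcome is analysed as an unadjusted change score, its variance exceeds that of the baseline-adjusted follow-up count. With equal SDs the excess is 33% to 100% for rho between 0.5 and 0, and it shrinks to 3% at rho 0.95. The direction is certain. The size is not, and rests on a low rho that is plausible for a transient finding but undocumented. The simulated figures compare linear analyses on the difference scale, so they indicate the gain to expect from a count model but do not measure it.

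The consequence is lost precision and sensitivity to chance imbalance on a secondary outcome. The fix does not make the comparison well powered. Separately, the synopsis and sections 3.2 and 5.3 define the enhancement outcome differently, and that needs settling whatever analysis is chosen.

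**What to change.** - In sections 3.2 and 5.3, define the outcome as the number of enhancing lesions on the follow-up scan, and say which scan that is for completers and for early withdrawals.
- Name one count model, for example negative binomial, with the week-0 count as a prespecified covariate in a stated form, used whatever baseline imbalance is observed. Exempt this covariate from the conditional rule in section 12.3. Show the raw change descriptively.
- Reconcile this with the synopsis: state which of the count and the proportion with enhancement is the secondary outcome, and label the other as supportive.
- Give a rule for participants with no contrast scan at week 0. Their follow-up count, if available, stays defined, whereas a change score would lose them. Only the covariate has to be handled.
- For T2 volume, baseline adjustment may be added for consistency, without a claim of gain.

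The cost is wording, the missing-baseline rule and about 1% of variance for one degree of freedom. The week-0 brain MRI is already scheduled for everyone, so no scan or visit is added. A negative binomial model reports a rate ratio rather than a difference, so the effect measure should be stated too.
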